4. ESTIMATED DURATION OF THE STUDY

3 years enrollment, 2 years data analysis (5 years total)

5. LAY LANGUAGE SUMMARY OR SYNOPSIS (no more than one paragraph)

Anorexia nervosa (AN) is an eating disorder associated with intense fear of weight gain, food refusal, and severe weight loss. AN has the highest mortality rate among the psychiatric disorders; however, little is known about biomarkers, and no medication has been approved for AN. Brain reward pathways have a direct impact on the drive to eat, and a variety of neuroimaging studies have suggested altered reward processing in AN. The neurotransmitter dopamine has a central role in the reward circuitry to drive food approach, and the dynamic interplay between dopamine receptor response and food restriction could have implications for the pathophysiology of AN. In this application, we will develop a study protocol and gather pilot data to identify whether specific dopamine D2 challenge drugs can modulate PE response and reversal learning in AN. In this randomized placebo controlled trial we will apply a dopamine D2 receptor agonist, D2 receptor antagonist and placebo to healthy controls and individuals with AN to test their effects on brain reward processing and reversal learning. We expect that those challenge drugs will lead to opposite brain and behavioral response and directly support the involvement of those receptors in brain function in AN. This research will be important to develop neurotransmitter specific pharmacological treatments for AN.

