Subjects who meet eligibility criteria based on the results of the questionnaires and phone bioscreen will be invited to the in-person interview with the PI at the UC San Diego Health Eating Disorders Center for Treatment and Research. At the start of the study visit, the PI or research coordinator will review the consent form with the subject, will answer any questions about the study and will assess comprehension of the study procedures, benefits, and risks. Subjects will then sign a new consent form and a signed and dated copy of the completed consent form will be given to the subject.

[name] will meet with each subject to complete the diagnostic assessment (SCID-5) and comprehensive medical interview with the subject to determine study eligibility.

After eligibility is confirmed, the subject will complete a swallow test where she will be given an empty pill capsule and will be asked to swallow to make sure she will not have any issues with the size of the medication capsules. If the subject cannot swallow this size capsule or feels she will not be able to, she may be withdrawn from the study at that point.

The subject will be scheduled for the Pre-Scan Visit and 3 MRI scans. The MRI scans will be scheduled 2 to 4 days apart (3 days apart is ideal).

Pre-Scan Visit

Location: Altman Clinical Trials Research Center ([name])

Subjects will complete a pre-scan visit at ACTRI to complete a blood draw and electrocardiogram (EKG). This visit will occur no more than 1 week before Study Visit 1 is scheduled. At this visit ACTRI research nursing staff (certified phlebotomist) will complete the blood draw (about 2 tablespoons blood). An EKG will be performed, and results of the EKG and blood tests will be sent to the PI for review. The following tests will be processed through the Center for Advanced Laboratory Medicine (CALM): Creatinine; BUN; electrolytes; serum pregnancy test. If the PI feels the results are out of range he may withdraw the subject from the study.

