Special Pharmacological Considerations. Bromocriptine is an anti-Parkinson medication available in the US. An investigational new drug (IND) application to the Federal Drug Administration (FDA) has been approved, IND # 141908. Amisulpride is an antipsychotic not freely available in the US; however, it can be purchased via Sanofi France as in previous studies (Admon et al., 2017). We have received an IND from the FDA, which allows for legal import of amisulpride. Both medications have a plasma peak of 3 hours, and fMRI will begin for all sessions at that time point after taking active drug or placebo. The half-lives for amisulpride of 12 hours, and 2-8 hours for bromocriptine are short enough to allow 3 days in between studies to suffice the 5 half-lives

rule for medication elimination from the body (neither medication has active metabolites) (Bergemann et al., 2005; Holt et al., 2010; Schatzberg and Nemeroff, 2013).

Handling of Study Medication

Storage Location: UC San Diego Health Eating Disorders Center for Treatment and Research, [name] (PI Office, [name])

Medications will be stored in a locked cabinet in the research office of the PI. That office is embedded in the UC San Diego Health Eating Disorders Research Program office suite, which is locked. Each study drug will be labeled with the statement “Caution: New Drug—Limited by Federal (or United States) law to investigational use.” (§312.6 Labeling of an investigational new drug.).

A randomization protocol will be developed ahead of the study using Research Randomizer (<https://www.randomizer.org>). The PI will randomize the study days for the three medications. A master file with the randomization of medication per subject will be kept by the study monitor ([name]).

While the tablets look slightly different, subjects will not be told what type of medication they receive on either day. Study participants have been drug naïve to any of the study medications, and we do not expect recognition. It is uncertain what specific effects each medication will have on brain function and there will therefore be no implicit bias.

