Each subject will complete three MRI scan days (Study Visit 1, Study Visit 2, and Study Visit 3). On each day, the subject will consume one of the three medications (amisulpride, bromocriptine or placebo). Each subject will complete a baseline scan (P-fMRI), Amisulpride scan (A-fMRI), and Bromocriptine scan (B-fMRI) spaced 3 days apart (2 to 4 day acceptable range). This randomized study has 6 medication study arms listed below:

On the morning of each study day, the PI or other study staff not running the fMRI scanning procedures will provide the study subjects the medication as per randomization. Other study personnel that will run the fMRI scanning procedures will be kept blinded from the applied medication. This will help reduce bias by the study personnel.

There are no rater applied assessments on the study days so there is no rater bias based on the personnel end. The fMRI data are objective and thus unbiased.

The investigator will not supply the investigational drug to any person not authorized under this part to receive it. (§312.61 Control of the investigational drug.)

Neither study drug is a controlled substance. Nevertheless, the study medication packages with the investigational drugs will be in a securely locked, substantially constructed cabinet, in the PI’s office, which is within an office suite that is locked and accessible only to the research personnel.

Should the subject have a serious adverse reaction that required emergency treatment, the PI would be contacted and the blinding of the medication order would be broken in order to allow adequate treatment of the patient by emergency department staff.

Each subject will be randomized to one of the following groups:

1.

Scan 1: P-fMRI
Scan 2: A-fMRI
Scan 3: B-fMRI

2.

Scan 1: P-fMRI
Scan 2: B-fMRI
Scan 3: A-fMRI

3.

Scan 1: A-fMRI
Scan 2: P-fMRI
Scan 3: B-fMRI

4.

Scan 1: A-fMRI
Scan 2: B-fMRI
Scan 3: P-fMRI

5.

Scan 1: B-fMRI
Scan 2: P-fMRI
Scan 3: A-fMRI

6.

Scan 1: B-fMRI
Scan 2: A-fMRI
Scan 3: P-fMRI

Medication dosage

Amisulpride – Single Dose 400 mg and scan 3 hours post ingestion

Bromocriptine – Single Dose 1.25 mg and scan 3 hours post ingestion

Amisulpride

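### Products that look different are given to the same woman across three visits, so the subject blind rests on silence and drug-naivety and expectancy can enter the drug–placebo contrasts

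*Combined protocol and SAP*

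**What the plan says.** Under Handling of Study Medication, Section 9 concedes a visible difference and offers three protections. The first is silence: "While the tablets look slightly different, subjects will not be told what type of medication they receive on either day". The second is lack of prior exposure: "Study participants have been drug naïve to any of the study medications, and we do not expect recognition". The third is an argument from uncertainty: "It is uncertain what specific effects each medication will have on brain function and there will therefore be no implicit bias".

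The same section gives every woman all three products, counting placebo as one of the three medications, on scan days about 3 days apart (2 to 4 accepted), in one of six orders.

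On personnel, "the PI or other study staff not running the fMRI scanning procedures will provide the study subjects the medication as per randomization", while "Other study personnel that will run the fMRI scanning procedures will be kept blinded from the applied medication". The PI generates the randomised order, and a master file is held by the study monitor. The visit descriptions in Section 9 have the research assistant administer the drug and take vital signs before and after the scan. Section 15 (Data and Safety Monitoring Plan) gives the data analysis to the PI, with some research assistant support.

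On dosage form, the screening text for both recruitment routes describes a swallow test with an empty capsule, to "make sure she will not have any issues with the size of the medication capsules". Over-encapsulation, a matched placebo, opaque packaging and a treatment-guess question are not described anywhere.

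**The concern.** The hypotheses under Aims 1 and 2 compare each drug with placebo within the same women. If a woman can tell that today's product is not the one she took last time, she can form a belief about which day is which, helped by any nausea or dizziness she has been told to expect. Choices in a win/lose reversal task, and reward responses more generally, may shift with that belief. A shift of this kind would be read as a dopamine D2 effect.

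Section 9 answers that fMRI data are objective. That addresses measurement by staff. It does not address what a woman's own belief does to her behaviour or brain response in the scanner.

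**Working it through.** No figure in the plan decides this point, so the check is mainly of text, followed by one piece of algebra and one illustration.

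**1. The three protections against the design.**
- *Not being told* protects only if the products cannot be told apart. The plan says they look different.
- *Drug-naivety* stops a woman recognising a product she knows. In a crossover she needs no prior knowledge, because she sees the products in turn.
- *Uncertainty of effect* is set against Section 5, "We expect that those challenge drugs will lead to opposite brain and behavioral response", and against Section 6, which gives a direction for each drug relative to placebo. The plan does hold directional expectations, so this argument does not support a conclusion of no bias.

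**2. Whether randomised order helps.** Write a woman's response as subject effect + period effect + τ(product) + e(product), where e is the shift due to what she believes about that product. With the six orders used equally, period effects cancel in the drug–placebo contrast and leave

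[τ(drug) − τ(placebo)] + [e(drug) − e(placebo)].

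The second bracket is indexed by product, as the drug effect is. Randomising the order leaves it in place.

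**3. Tablets and capsules.** Handling of Study Medication speaks of tablets; the swallow-test text speaks of capsules. If all products are given in identical capsules, the sentence about differing tablets is wrong. If they are not, the products are distinguishable. The documents do not say which.

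**4. Who knows the allocation.** Only staff running the scans are declared blinded. The dispenser works from the randomisation. The PI randomises, may dispense and analyses. The research assistant administers the drug and supports the analysis; whether that person is blinded is not stated. Section 9 says there are no rater-applied assessments on study days, but Section 25 has research staff complete a symptom checklist at each study visit.

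**5. Illustration of the consequence.** Assume no true drug effect, a two-sided 5% paired t-test, and an expectancy shift of b standard deviations of the within-woman difference (noncentrality b√n). The value of b is an assumption. The 20 per group comes from the plan's power statement, which concerns AN versus controls. The 22 assumes that the 44 planned completers split equally.

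| b | rejection rate, n = 20 | rejection rate, n = 22 |
|---|---|---|
| 0 | 5.0% | 5.0% |
| 0.1 | 7.1% | 7.3% |
| 0.2 | 13.6% | 14.6% |
| 0.3 | 24.7% | 26.9% |
| 0.5 | 56.5% | 60.9% |

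For example, at n = 20 and b = 0.2 the noncentrality is 0.2 × √20 = 0.89. The table shows how sensitive the test is. It does not estimate b.

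**The case against.** The strongest reply is that noticing a slight difference is not the same as identifying a drug. At Visit 1 there is nothing to compare: each product comes first in two of the six orders, so with equal allocation a third of its scans fall there. Nausea is expected with either drug and does not separate them. The directional expectations in Sections 5 and 6 are the investigators', and the consent pages are not available, so what the women are told about direction is unknown. The capsule wording may mean that masking is already intended. The taste task is cue–taste conditioning with no choice described, and mood, craving and taste ratings are not outcomes named in the hypotheses under Aims 1 and 2.

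Much of this stands as a limit on size. It does not remove the problem. Two thirds of scans still follow at least one other product. Separating either drug from placebo is enough to affect the contrasts, even if the drugs are not told apart. Reversal learning, which does involve choices, is a hypothesis outcome. If masking is intended, the plan should say so.

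A reader might also infer that a dispenser's blind has been broken, or that anyone who sees a product knows the arm. The documents do not support either. No dispenser's blind is claimed, and appearance reveals the arm only to someone who knows which appearance belongs to which product.

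**Conclusion.** The concern holds as a weakness in the subject blind. The plan concedes a visible difference, the crossover lets each woman see it, no masking of appearance is described, and the stated defences do not protect the drug–placebo contrasts. The conclusion assumes that the sentence about tablets describes what is actually given; the capsule wording leaves that open. Separately, allocation and analysis are not kept apart, because the PI randomises, may dispense and analyses.

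The size is unknown. A reader might multiply a share of women who identify the day (0.3 to 0.7) by an expectancy effect (0.2 to 0.4 SD) and report a bias of 0.06 to 0.28 SD. Neither input is in the documents and no sign is justified, so that range should not be presented as a finding. For a pilot meant to inform later studies this is a cheap improvement worth making; it cannot be made after the scans are done.

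**What to change.** 1. In Section 9, Handling of Study Medication, reconcile tablets with capsules. State that amisulpride, bromocriptine and placebo are supplied in identical opaque capsules of the swallow-test size, coded by subject and visit number and carrying the investigational-drug caution statement required by Sections 9 and 25.
2. Delete the sentence claiming no implicit bias.
3. State for each role (dispenser, research assistant, scanning staff, analyst) whether it is blinded. Keep drug labels coded until ROI extraction and the analysis are fixed.
4. Add one item to the existing Post MRI Questionnaire asking which condition the woman thinks she received, and report guesses by condition, descriptively only. Do not repeat the contrasts by correct versus incorrect guess. A true drug effect can itself produce a correct guess, and with 22 women per group (equal split assumed) and 30% to 70% correct, a stratum would hold about 7 to 15 women (0.3 × 22 = 6.6; 0.7 × 22 = 15.4).

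Cost: encapsulating at least 44 × 3 = 132 doses, more with dropouts and the repeat visits allowed in Section 20; one questionnaire item; and a check that the capsule is compatible with the planned 3-hour interval before scanning. Identical capsules would not prevent unmasking through side effects; the guess item would give some indication of how far that happens.

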9. RESEARCH DESIGN AND METHODS

Overview of Study Procedures:

In this randomized, placebo controlled trial subjects will complete a battery of self-assessments, a diagnostic assessment, and a pre-scan visit in order to determine eligibility. After eligibility is confirmed, subjects will be randomized to one of the six study arms that will determine the order in which the study medication is administered the morning of the MRI scans. Subjects will complete 3 MRI scans spaced approximately 3 days apart. Functional MRI will be performed and brain response will be measured while subjects complete a taste reward task and a reversal learning task. Details of the outcome measures and study procedures are listed below:

Outcome Measure(s):

Prior to completing the fMRI scans, each subject will complete the Diagnostic interviews and Self-Assessments listed below:

	Name	Abbreviation	Area assessed	Minutes
Diagnostic Interviews				
	Structured Clinical Interview for DSM-5 Diagnoses	SCID 5	Half structured diagnostic interview for Axis I Disorders	45-90
Self-assessments (Questionnaire Packet)				
	Spielberger State-Trait Anxiety Scale-Version Y	STAI-Y	State and trait anxiety	10
	Beck Depression Inventory	BDI-II	Assess the cognitive, behavioral, affective, and somatic symptoms associated with depression.	5
	Eating Expectancy Inventory	EEI	Measures cognitive expectations for eating	5
	Food Cravings Questionnaire - Trait	FCQ-T	Measures intensity of state and trait food cravings	10
	Intolerance of Uncertainty Scale	IUS	Measures intolerance of uncertainty	5
	Eating Disorder Examination	EDE-Q	Measures restraint and eating, weight and shape concern	15

	Temporal Experience of Pleasure Scale	TEPS	Measures anticipatory and consummatory experiences of pleasure for food and nonfood items	5
	Eating Disorders Inventory -3	EDI-3	Core ED symptoms	15
	Temperament and Character Inventory	TCI	Personality and temperament	30
	Sensitivity to Punishment and Sensitivity to Reward Questionnaire	SPSRQ	Reward and Punishment Sensitivity	5
	Beck Cognitive Insight Scale	BCIS	Subject beliefs and degree of confidence in beliefs	5
	Schedule for Assessment of Insight – Modification for Eating Disorders	SAI-ED	Insight into eating disorder symptoms	3
	Behavioral Inhibition Scale/Behavioral Activation Scale	BIS/BAS	Reward and Punishment Sensitivity	5
	Parental Bonding Instrument	PBI	Parental bonding	5
	Adverse Childhood Effects Questionnaire	ACEs	Childhood trauma	5
Scan Day Assessments				

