Amisulpride. Amisulpride (4-amino-N-[(1-ethylpyrrolidin-2-yl)methyl]-5-ethylsulfonyl-2-methoxy-benzamide has a bioavailability of 48% and a half-life of about 12 hours (Rosenzweig et al., 2002). It binds selectively (<https://pubchem.ncbi.nlm.nih.gov/compound/2159>) to DA D(2) and D(3) receptors in the limbic system. It reaches its peak plasma levels after 1 hour and has a second peak after 3 hours. Amisulpride does not have active metabolites (Bergemann et al., 2005). Low doses of amisulpride block presynaptic D(2)/D(3)-dopamine autoreceptors, thereby enhancing dopaminergic transmission, whereas higher doses block post-synaptic receptors, thus inhibiting DA activity (Leucht et al., 2002). In this application, we will apply a high dose to take advantage of the DA D2 receptor blocking effects of amisulpride. We are orienting our dosing on previous research using a single dose of 400mg amisulpride to block post-synaptic DA D2 receptors during fMRI (Kahnt and Tobler, 2017). That dosage showed good tolerability (Rosenzweig et al., 2002). Whether this dose is tolerable in an AN population has not been established and is a goal of this study. Establishing pharmacokinetics with plasma levels will also be important but will be part of future larger studies.

Bromocriptine. Bromocriptine is a semisynthetic, ergot alkaloid with anti-Parkinson and lactation inhibitory activities. Bromocriptine selectively binds to and activates postsynaptic DA D2-like receptors in the central nervous system (CNS), its half-life is between 2 and 8 hours, and it does not have active metabolites (<https://pubchem.ncbi.nlm.nih.gov/compound/31101>). Bromocriptine has a bioavailability of 28% and reaches its peak plasma level around 3 hours after ingestion (Holt et al., 2010). Bromocriptine has been used in fMRI previously and modulated reward and reversal learning (Cools et al., 2009). Effects of DA synthesis capacity will be tested in future larger studies. We will apply a single dose of 1.25mg bromocriptine, which was effective in manipulating both fMRI and behavior results (Cools et al., 2009; Lissek et al., 2018).

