11. RECRUITMENT AND PROCEDURES PREPARATORY TO RESEARCH

Selection of study population

Subjects will be recruited from UC San Diego Health Eating Disorders Center for Treatment and Research, as well through local advertisements. Subjects will reflect generally the socioeconomic and ethnic distribution of California as many patients come from the entire state.

Patient accrual

All subjects will be accrued locally. *Individuals with AN* ages 18-29 years will be recruited primarily from UC San Diego Health Eating Disorders Center for Treatment and Research, which treats per year across residential, day hospital, and intensive outpatient program more than 100 adult patients with anorexia nervosa. Willingness to participate and study eligibility ranges between 40 and 60%. We will study subjects within 1-2 weeks of admission in order to avoid the confounding effects of acute starvation or dehydration. *Healthy controls* ages 18-29 years will be recruited through local advertisements. Healthy controls will be studied during the first ten days of the menstrual cycle to keep hormonal variation low.

AN Subjects from UC San Diego Health Eating Disorders Center for Treatment and Research: [name] is an attending physician at the UC San Diego Health Eating Disorders Center for Treatment and Research program. Any eligible patients who are admitted into these programs will be screened and approached by the PI and/or research staff regarding their participation in the study. Prior to approaching the patient, [name] and/or his staff will obtain permission from the patient's individual therapist prior to making contact with the patient to describe the research opportunity. The research staff will complete the initial screening to determine eligibility. After determining initial eligibility, the PI or research staff will obtain consent from these individuals in person. All diagnostic assessments, questionnaires, and procedures will be conducted in the PI's/Research staff's private office (at the UC San Diego Health Eating Disorders Center for Treatment and Research), Altman Clinical Research Institute, or at the Sharp and Children's MRI Center (for the scanning procedures).

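### The accepted 2-day gap between scans breaks the plan's own five-half-life washout rule for amisulpride (about 48 h against 60 h)

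*Combined protocol and SAP*

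**What the plan says.** Under Special Pharmacological Considerations (Section 9), the half-lives of 12 h for amisulpride and 2 to 8 h for bromocriptine are described as "short enough to allow 3 days in between studies to suffice the 5 half-lives" rule for elimination. Under Handling of Study Medication, the three sessions are "spaced 3 days apart (2 to 4 day acceptable range" in days. The Timeline repeats that tolerance for community participants and for treatment-center participants: "The MRI scans will be scheduled 2 to 4 days apart (3 days apart is ideal", in each case. The Overview of Study Procedures gives the target only: "Subjects will complete 3 MRI scans spaced approximately 3 days apart".

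Dosing is tied to the morning ("On the morning of each study day, the PI or other study staff not running the fMRI scanning procedures" give out the drug), and each scan starts 3 h after the dose. No section sets a longer minimum after the amisulpride session. The Data Analysis Plan uses repeated measures ANCOVA and names no period, sequence or carryover term.

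**The concern.** The washout argument is made at one interval, 3 days, but staff may book 2 days without deviating from the protocol. If the rule fails there, the stated washout property does not hold over the whole accepted range.

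This matters because the trial is a three-period crossover and the drug hypotheses in Aims 1 and 2 are contrasts with placebo. Residual amisulpride would fall on the placebo or bromocriptine scan that follows it. The direction of such an effect cannot be assumed. The protocol says "Low doses of amisulpride block presynaptic D(2)/D(3)-dopamine autoreceptors, thereby enhancing dopaminergic transmission", whereas higher doses inhibit dopamine activity, and it gives no threshold between the two. With no carryover term in the analysis, the washout interval is the only stated protection.

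**Working it through.** **Inputs**, all from Section 9: amisulpride half-life about 12 h and bromocriptine 2 to 8 h (Dopamine Challenge Drugs); five-half-life rule (Special Pharmacological Considerations); gap of 3 days planned and 2 to 4 accepted, single 400 mg amisulpride dose (Handling of Study Medication); dose 3 h before the scan (Timeline).

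**Formulas.** Time required = 5 × half-life. Half-lives elapsed = hours / half-life. Fraction left = 0.5^(hours / half-life), assuming first-order elimination.

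**The plan's own figure.** At 3 days, amisulpride has 72 / 12 = 6.0 half-lives and bromocriptine, at its longest half-life, 72 / 8 = 9.0. Both exceed 5, so the statement about 3 days is correct.

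**The rest of the accepted range, amisulpride.** Required: 5 × 12 = 60 h.

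| Interval | Hours | Half-lives | Left | Share of 400 mg | Rule met |
|---|---|---|---|---|---|
| 2 days, dose to dose | 48 | 4.0 | 6.25% | 25 mg | no |
| 2 days, dose to next scan | 51 | 4.25 | 5.3% | 21 mg | no |
| Limit of the rule | 60 | 5.0 | 3.1% | 12.5 mg | yes |
| 3 days, dose to dose | 72 | 6.0 | 1.6% | 6.25 mg | yes |
| 4 days, dose to dose | 96 | 8.0 | 0.4% | 1.6 mg | yes |

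Two days are 60 − 48 = 12 h short and leave twice the residual that the rule allows.

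**Bromocriptine at 2 days.** The longest requirement is 5 × 8 = 40 h, below 48 h. The rule is met.

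**Clock time.** fMRI Study Procedures sets arrival at 6 to 7 am, or 3 h before the scan. Within 6 to 7 am, a 2-day gap is 47 to 49 h. If morning dosing could run from 6 am to noon (noon is an assumption), a 2-day gap is 48 ± 6 = 42 to 54 h dose to dose (8.8% to 4.4% left), or 45 to 57 h to the scan. All of these are below 60 h. A 3-day gap is then 72 ± 6 = 66 to 78 h (2.2% to 1.1% left), always above 60 h.

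**Half-life.** The rule holds at 48 h only if the half-life is at most 48 / 5 = 9.6 h, or 51 / 5 = 10.2 h counting to the scan. At 72 h it holds up to 72 / 5 = 14.4 h. If the stated 12 h really covers 10 to 14 h (an assumption), 0.5^4.8 = 3.6% to 0.5^3.43 = 9.3% is left at 48 h.

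**Where it can occur.** Amisulpride is directly followed by placebo in sequences 3 and 6 and by bromocriptine in sequences 1 and 4, which is 4 of the 12 gap positions. With equal-probability assignment (assumed) and 44 completers, 44 × 4/6 ≈ 29 of 44 × 3 = 132 scans directly follow amisulpride. That is a ceiling: the share at 2 days is unknown and could be zero. A scan two visits after amisulpride is at a nominal 96 h or more and meets the rule.

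**The case against.** The strongest reply is that the plan makes no arithmetic error. It applies the rule to 3 days, where it holds, and nowhere claims that 2 days satisfy it. Three days is the target throughout. This is right as a description, and it makes the point one of consistency between a rule and a tolerance. It does not remove the mismatch, because 2 days is expressly acceptable.

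The second reply is that the design blunts any carryover. If the six sequences are balanced, and carryover is additive and similar in size after equally long gaps, it affects one-third of placebo scans and one-third of bromocriptine scans, so it cancels in the bromocriptine-placebo contrast (Aim 1). In the amisulpride-placebo contrast (Aim 2) the mean shift is at most one-third of the carryover effect, scaled by the share of 2-day gaps. This is a fair reason to expect little bias. It depends on balance, though, and the randomization text names no blocking.

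A third reply is that 2 days apart could mean two full days in between, that is 72 h. The scheduling sentence does not read naturally that way, and if it was meant, the wording needs correcting.

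Finally, 5% to 6% against 3% is a small difference in a feasibility pilot, and the tolerance may be a deliberate scheduling choice. The small size stands and sets the severity. The protocol does not describe the tolerance as a trade-off.

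**Conclusion.** The concern holds, as a minor one. On the plan's own half-life, the 2-day end of the accepted range gives 4.0 to 4.25 amisulpride half-lives against the 5 that the plan relies on, with 5.3% to 6.25% of the drug left against 3.1%. The assumptions are first-order elimination, the stated 12 h half-life and morning dosing; no morning slot up to noon closes the gap. The documents give no half-life in anorexia nervosa, and plasma levels are left to later studies, so the trial will not show whether elimination was faster or slower.

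The planned 3-day interval, bromocriptine, and scans two visits after amisulpride all meet the rule. These figures are a breach of the plan's own criterion, not evidence of material carryover.

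**What to change.** Change the accepted range from 2 to 4 days to 3 to 4 days in the three places where it stands: the two Timeline scheduling paragraphs (community and treatment-center participants) and Handling of Study Medication. Apply it to every gap and not only after amisulpride, so that the spacing of visits does not reveal the drug.

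If 2-day gaps have already occurred, record the hours from the amisulpride dose to the next scan and run one sensitivity analysis with a term for amisulpride as the previous drug. Fit it as a mixed model, because the term changes between scans within a participant. A plain previous-drug term pools 2-, 3- and 4-day gaps. Coding it to mark only intervals under 60 h targets the shortfall better, though few scans may qualify and a null result would be weak reassurance.

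The cost is scheduling flexibility, judged against two windows in Section 11.

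- Controls: "Healthy controls will be studied during the first ten days of the menstrual cycle to keep hormonal variation low". The latest first scan moves from cycle day 10 − 4 = 6 with 2-day gaps to 10 − 6 = 4 with 3-day gaps. With two 4-day gaps it is 10 − 8 = 2, as under the current range.
- Anorexia nervosa: "We will study subjects within 1-2 weeks of admission in order to avoid the confounding effects of acute starvation or dehydration". If this means days 7 to 14, the first scan must fall on day 7 or 8 (14 − 6 = 8), against days 7 to 10 (14 − 4 = 10) with 2-day gaps. Two 4-day gaps would need a start by day 14 − 8 = 6, so they do not fit, which is already true now. If it is only an upper limit of two weeks, a first scan by day 8 suffices, or by day 6 with two 4-day gaps.

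The patient group is the harder one to schedule, so a few sessions may need rebooking. The text change itself is one line in each of three places.
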